Table 1 Protocol Amendment 2 - Summary of Changes

Section Number(s)	Section Title(s)	Description of Change(s)
NA	Title Page	Updated name and contact of the sponsor
2.2	Subject Inclusion Criteria	Updated inclusion criteria 5 to reflect standard text for the V503 program. Added instructions for contraceptive use for women with no childbearing potential.

V503-004-02

15-Mar-2017

049WHD

ABBREVIATIONS AND DEFINITIONS

AE	adverse event
ANSS	all type-specific naïve subjects with serology
AW	adult women
cLIA	competitive Luminex® immunoassay
CRA	clinical research associate
e-CRF	electronic case report form
CSP	clinical study protocol
CSR	clinical study report
EDC	electronic data capture
EU	European Union
GMT	geometric mean titre
HPV	human papillomavirus
ICF	informed consent form
IEC	independent ethics committee
IMP	investigational medicinal product
IRT	Interactive response technology
mAbs	monoclonal antibodies
mMU/mL	milli merck units per millilitre
PPI	per protocol immunogenicity
qHPV	quadrivalent human papillomavirus vaccine
SAE	serious adverse event
VLP	virus-like particles
eVRC	Electronic vaccination report card
YAW	young adult women
9vHPV	9-valent (6/11/16/18/31/33/45/52/58) human papillomavirus vaccine

1.0 SUMMARY

1.1 Title

An Open-Label Phase III Clinical Trial to Study the Immunogenicity and Tolerability of GARDASIL®⁹ (A Multivalent Human Papillomavirus [HPV] L1 Virus-Like Particle [VLP] Vaccine) in Adult Women (27- to 45-Year-Olds) compared to Young Adult Women (16- to 26-Year-Olds)

1.2 Indication

Prevention of cervical, vulvar, vaginal, and anal cancers and related precancers, external genital lesions, Pap test abnormalities, and persistent infection caused by HPV Types 6, 11, 16, 18, 31, 33, 45, 52, and 58.

1.3 Summary of Rationale

GARDASIL®⁹¹ is a prophylactic 9-valent human papillomavirus (9vHPV) (Types 6, 11, 16, 18, 31, 33, 45, 52, and 58) L1 virus-like particle (VLP) vaccine that is comprised of VLPs of the 4 human papillomavirus (HPV) types (Types 6, 11, 16, and 18) contained in GARDASIL®², plus the VLPs of 5 additional oncogenic HPV types (Types 31, 33, 45, 52, and 58). This vaccine offers the potential of significant prophylactic cancer coverage in addition to that already provided by GARDASIL®, with an increase in overall cervical cancer coverage from approximately 70% to 90%.

GARDASIL®⁹ received marketing authorization in the European Union (EU) in June 2015 for active immunization of individuals from the age of 9 years against premalignant lesions and cervical, vulvar, vaginal and anal cancers caused by vaccine HPV types and genital warts (*Condyloma acuminata*) caused by specific HPV types.

The efficacy of GARDASIL® is relevant to GARDASIL®⁹ since the vaccines are manufactured by a similar process and contain 4 of the same HPV L1 VLPs.

As summarized in the GARDASIL®⁹ Summary of Product Characteristics, the efficacy of GARDASIL®⁹ was compared with that of the quadrivalent HPV (qHPV) vaccine with respect to HPV types 6, 11, 16, and 18. The population included girls and women between 16 to 26 years (Protocol 001) and girls between 9 to 15 years (Protocol 009). Immune responses for

¹ GARDASIL®⁹ (Human Papillomavirus 9-valent Vaccine, Recombinant) is a registered trademark of Merck Sharp & Dohme Corp., a subsidiary of Merck & Co., Inc., Whitehouse Station, New Jersey, U.S.A.

² GARDASIL [Quadrivalent Human Papillomavirus (Types 6, 11, 16, 18) Recombinant Vaccine] is a registered trademark of Merck & Co., Inc., Whitehouse Station, New Jersey, U.S.A. GARDASIL is also known as SILGARD in some countries. SILGARD is a trademark of Merck & Co., Inc., Whitehouse Station, New Jersey, U.S.A.

GARDASIL®9 were found to be non-inferior to immune responses for GARDASIL®. Of the subjects receiving GARDASIL®9, 99.6% to 100% became seropositive for antibodies against all 9 vaccine types by Month 7 across all groups tested. GARDASIL®9 was also found to be efficacious in preventing HPV 31-, 33-, 45-, 52-, and 58-related persistent infection and disease in girls and women between 16 to 26 years (Protocol 001).

Clinical study results suggest that women older than 26 years of age without evidence of prior exposure to the vaccine types can benefit from GARDASIL®.^{3,4} The long-term effectiveness and safety of the GARDASIL® vaccine in older women have also been found to be high.⁵ Studies also suggest that subjects who have been previously exposed to HPV might benefit from HPV vaccination.^{6,7} In several EU countries such as Austria, Italy, Ireland, and Germany, there is acknowledgement of HPV vaccine benefit after HPV exposure and/or treatment. Canada and Australia have recommended the qHPV vaccine for women between 27 to 45 years of age.

Studies with GARDASIL®9 in women older than 26 years of age have not been conducted.

This study is designed to assess the safety and immunogenicity of GARDASIL®9 in 27- to 45-year-old women, to complete the evaluation of GARDASIL®9 in the extended age range of female subjects for whom GARDASIL® was proven to be effective. This study is primarily powered to demonstrate the non-inferior immunogenicity of GARDASIL®9 in 27- to 45-year-old women, compared with 16- to 26-year-old women, the population in which GARDASIL®9 has been demonstrated to be effective, with respect to the 7 oncogenic HPV types (Types 16, 18, 31, 33, 45, 52, and 58).

1.4 Summary of Study Design

This study will enrol a total of approximately 1,200 subjects, i.e., 600 women 16- to 26-years-old and 600 women 27- to 45-years-old, all of whom have not yet received a prophylactic HPV

³ Muñoz N, Manalastas R Jr, Pitisuttithum P, Tresukosol D, Monsonego J, Ault K, et al. Safety, immunogenicity, and efficacy of quadrivalent human papillomavirus (types 6, 11, 16, 18) recombinant vaccine in women aged 24–45 years: a randomised, double-blind trial. Lancet. 2009 Jun 6;373:1949-57.

⁴ Castellsagué X, Muñoz N, Pitisuttithum P, Ferris D, Monsonego J, Ault K, et al. End-of-study safety, immunogenicity, and efficacy of quadrivalent HPV (types 6, 11, 16, 18) recombinant vaccine in adult women 24–45 years of age. Br J Cancer. 2011;105(1):28-37.

⁵ Luna J, Plata M, Gonzalez M, Correa A, Maldonado I, Nossa C, et al. Long-term follow-up observation of the safety, immunogenicity, and effectiveness of Gardasil™ in adult women. PLoS ONE. 2013;8(12):e83431.

⁶ Joura EA, Garland SM, Paavonen J, Ferris DG, Perez G, Ault KA, et al. Effect of the human papillomavirus (HPV) quadrivalent vaccine in a subgroup of women with cervical and vulvar disease: retrospective pooled analysis of trial data. BMJ. 2012 Mar 27;344:e1401.

⁷ Kang WD, Choi HS, Kim SM. Is vaccination with quadrivalent HPV vaccine after loop electrosurgical excision procedure effective in preventing recurrence in patients with high-grade cervical intraepithelial neoplasia (CIN2-3)? Gynecol Oncol. 2013 Aug;130(2):264-8.

vaccine. The study will provide a comparison of immunogenicity of GARDASIL®9 in 27- to 45-year-old women, with 16- to 26-year-old women, with respect to the 7 oncogenic HPV types (Types 16, 18, 31, 33, 45, 52, and 58). The responses to the two non-oncogenic HPV types included in the vaccine (Types 6 and 11) will be presented using descriptive statistics. The number of subjects to be enrolled in the study was determined based on the primary immunogenicity objective.

All subjects will be administered a standard 3-dose regimen (Day 1, Month 2, Month 6) of GARDASIL®9. Serum samples will be collected on Day 1 and Month 7 for anti-HPV 6, 11, 16, 18, 31, 33, 45, 52, and 58 antibody assays. The time point for comparison of immune responses will be Month 7, or approximately 4 weeks after the administration of the third dose. The safety/tolerability profile of the vaccine will be evaluated in all subjects in the study. Safety information will be collected on Day 1 through 1 month following the third vaccination or for a total of approximately 7 months for each subject.

The end of the study will be defined as when final report of study results is available.

1.5 Sample

This study will enrol healthy women in 2 age groups: 16- to 26-year-olds and 27- to 45-year-olds. Each age group will be further stratified into subgroups of 16- to 20-year-olds and 21- to 26-year-olds for young adult women (YAW) and 27- to 36-year-olds and 37- to 45-year-olds for adult women (AW). Enrolment will be monitored to make sure that no single age stratum (i.e., subgroup) exceeds 55% of the total sample of a given age group (i.e., enrolment in an age stratum will be stopped when around 330 subjects in that age stratum have been vaccinated).

1.6 Dosage/Dosage Form, Route, and Dose Regimen

Subjects will receive GARDASIL®9 (HPV 9-valent vaccine [recombinant, adsorbed]) administered as a 0.5-mL intramuscular injection on Day 1, Month 2 and Month 6. The vaccine formulation is summarized in [Table 2](#).

GARDASIL®9 is available as a suspension for injection. It appears as a clear liquid with white precipitate.

Table 2 Vaccine Formulation (0.5-mL Dose)

HPV 6 (mcg)	HPV 11 (mcg)	HPV 16 (mcg)	HPV 18 (mcg)	HPV 31 (mcg)	HPV 33 (mcg)	HPV 45 (mcg)	HPV 52 (mcg)	HPV 58 (mcg)	Total VLP (mcg)	AAHS [†] (mcg)
30	40	60	40	20	20	20	20	20	270	500

[†] AAHS, Merck Aluminum Adjuvant (amorphous aluminum hydroxyphosphate sulfate)

HPV, human papillomavirus; VLP, virus-like particle.

1.7 Study Flow Chart

Visit Windows (a):	Consent Visit	2 months after Day 1, ±3 weeks	6 months after Day 1, ±4 weeks	3 to 7 weeks after Month 6
Event/Test	Day 1 (Visit 1)	Month 2 (Visit 2)	Month 6 (Visit 3)	Month 7 (Visit 4) (b)
Obtain informed consent form / assent	+			
Informed Consent for Future Biomedical Research	+			
Assign screening number	+			
Review inclusion/Exclusion criteria (c)	+			
Collect medical history (past year)	+			
Collect demographics	+			
Collect height and weight	+			
Update Medical History (new conditions not already recorded as medical history or adverse events (AEs)		+	+	+
Review medications and non-study vaccines (d)	+	+	+	+
Pregnancy test (serum or urine) (e)	+	+	+	+
Blood sample for anti-HPV antibody testing (including retention serum) (10 ml of blood each time) (f)	+			+
Blood (DNA) for Future Biomedical Research (j)	+			
Collect oral temperature (g)	+	+	+	

Visit Windows (a):	Consent Visit	2 months after Day 1, ±3 weeks	6 months after Day 1, ±4 weeks	3 to 7 weeks after Month 6
Event/Test	Day 1 (Visit 1)	Month 2 (Visit 2)	Month 6 (Visit 3)	Month 7 (Visit 4) (b)
Assign allocation number	+			
Perform vaccination (Intramuscular; prefer deltoid muscle of non-dominant arm; do not give in buttocks)	+	+	+	
Provide electronic vaccination report card (eVRC)	+			
Review and collect eVRC data (h)		+	+	+
Review AEs, clinical follow-up for safety (i)	+	+	+	+

(a) To calculate visit windows, assume 1 month equals 30 days and 1 week equals 7 days.
 (b) Whenever possible, when a subject discontinues/withdraws prior to study completion, all applicable activities scheduled for the final study visit should be performed at the time of discontinuation except for serum collection for HPV testing.
 (c) A physical examination may be performed during Visit 1 if deemed necessary by the investigator to assess eligibility criteria.
 (d) See Section 3.2.2.2 for details of documentation times and time period restrictions for medications and non-study vaccines. If other non-study vaccines are administered at any time during the study, they should not be administered in the same limb as the study vaccine and must be appropriately documented.
 (e) The serum or urine pregnancy test will be performed per the manufacturer's instructions. A pregnancy test will be performed before administration of each dose of the study vaccine and at the final Month 7 visit on all subjects. The pregnancy test must be performed prior to serum collection for HPV testing at Day 1.
 (f) Blood sample for anti-HPV measurements must be collected prior to the first study vaccination. Serum must be shipped as specified by the Sponsor. The retention serum vial must remain at the study site until the Sponsor notifies the study site to ship the samples. Leftover main study serum sample will be stored for future biomedical research if the subject consents to the Future Biomedical Research.
 (g) If the subject has a fever (defined as an oral temperature of $\geq 37.8^{\circ}\text{C}$ or 100.0°F) within the 24-hour period prior to receiving a study vaccination, the subject should not receive study vaccine, and the vaccination visit should be rescheduled until after the fever has resolved. Oral temperature will be measured prior to each vaccination.
 (h) The investigator should instruct the subject to use the eVRC to document oral temperature in the evening after each study vaccination and daily, at the same time of day, for 4 days after each study vaccination. Additionally, injection-site and systemic adverse event(s) (AEs), concomitant medications, and concomitant vaccinations are to be documented in the eVRC starting after each study vaccination for a total of 15 days, including the day of vaccination (Day 1 to Day 15).
 (i) Observe subjects for at least 15 minutes after each vaccination for immediate untoward effects. Serious adverse events (SAEs), pregnancy events, and lactation events should be reported to the Sponsor's, within 24 hours. Adverse events and SAEs will be followed for 15 days and 30 days, respectively, after the last dose (i.e., after the third dose for subjects completing the vaccination schedule or after the last received dose in the event of the subject withdrawing).
 (j) Informed consent for future biomedical research samples must be obtained to collect the DNA sample.

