2.4 Study Design and Duration

2.4.1 Summary of Study Design

This is an international, multicentre; open-label, immunogenicity and tolerability study of GARDASIL®9 in 16- to 45-year-old women.

Approximately 1,200 healthy women, all of whom have not yet received a prophylactic HPV vaccine, will be enrolled in the study (i.e., 600 YAW between 16 to 26 years of age and 600 AW between 27 to 45 years of age). Each age group will be divided in 2 strata defined as 16- to 20-year-olds and 21- to 26-year-olds for YAW and 27- to 36-year-olds and 37- to 45-year-olds for AW. The immunogenicity data will be summarized by strata and age group, and the safety data will be summarized for 16- to 26-year-old women and 27- to 45-year-old women. All enrolled subjects will receive a 3-dose regimen (Day 1, Month 2, and Month 6) of GARDASIL®9. Serum samples will be obtained on Day 1 and Month 7 for anti-HPV 6, 11, 16, 18, 31, 33, 45, 52, and 58 testing. Immunogenicity analyses will be performed after all subjects have completed the Month 7 visit.

Medical history (past year) will be collected on Day 1 for all subjects. Oral temperature will be measured prior to each vaccination. Vital signs (height, weight, and oral temperature) will be collected on Day 1. Physical examination will be conducted on Day 1 if deemed necessary by the investigator.

Subjects will be monitored for safety and tolerability from Day 1 through 1 month following the third vaccination or for a total of approximately 7 months for each subject. A pregnancy test will be performed before administration of each dose of the study vaccine and at the final Month 7 visit on all subjects. The pregnancy test must be performed prior to serum collection for HPV testing at Day 1. Any subject with a positive pregnancy test at Day 1 will not be vaccinated and will not be allowed to participate in the study. Subjects with a positive pregnancy test after Day 1 will not be vaccinated with subsequent doses until resolution of the pregnancy as outlined in **Table 3**. Pregnant subjects who receive less than 3 vaccinations during the study will be offered the possibility to complete the vaccination course. Pregnancies and associated adverse experiences will be followed to outcome.

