3.5.4 Analysis Populations

3.5.4.1 Immunogenicity Analysis Populations

Per Protocol Immunogenicity Population

The per-protocol immunogenicity (PPI) analysis populations will serve as the primary populations of subjects for the analysis of immune responses to each of the 9 HPV types (6, 11, 16, 18, 31, 33, 45, 52, and 58). The PPI analysis populations are HPV type-specific, i.e., each HPV type has its own PPI analysis population. To be included in a particular HPV type-specific PPI analysis population, subjects must:

- Have received all 3 vaccinations of the correct dose of GARDASIL®9 within acceptable day ranges (See [Table 5](#)).
- Have evaluable serology results at Day 1 and Month 7 based on serum samples collected within acceptable day ranges (See [Table 6](#)).
- Be seronegative to the appropriate HPV type at Day 1.
- Have no protocol deviations that could interfere with the evaluation of subject's immune response to GARDASIL®9.

To be included in the PPI analysis population for HPV 6 and 11, subjects must be seronegative to both HPV 6 and 11 at Day 1. To be included in the PPI analysis population for any other vaccine HPV type, subjects need to be seronegative to that specific type at Day 1. The final determination of protocol deviation categories deemed as having potential to interfere with evaluation of immune response to GARDASIL®9 will be made prior to database lock and will be recorded in a separate study document.

Table 5 Acceptable Day Ranges for Vaccination Visits

Dose of 9vHPV Vaccine Scheduled for Injection	Protocol Specified Visit Window	Day Range for Inclusion in Statistical Analysis (Relative to Day 1[†])
Dose 1	Day 1 [†]	0
Dose 2	Month 2 ± 3 weeks	36 to 84
Dose 3	Month 6 ± 4 weeks	148 to 218
[†] Day 1 refers to the date when Dose 1 of the study vaccine is injected. For vaccinations after Day 1, the day ranges for inclusion in the statistical analysis are wider than the protocol-specified visit windows primarily to account for differences at the study sites in counting months (e.g., 1 calendar month versus 30 days versus 4 weeks).		
9vHPV, 9-valent human papillomavirus.		

Table 6 Acceptable Day Ranges for Collection of Serum Samples

Study Visit	Target Collection Day (Relative to Day 1[†])	Day Range for Inclusion in Statistical Analysis[†]
Day 1	0	-14 to 0 (Relative to Day 1) [‡]
Month 7	30 days after Dose 3	21 to 49 after Dose 3 [§]

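### Does a Month 7 visit as early as Day 21 after Dose 3 undermine the 30-day follow-up for serious adverse events?

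*Combined protocol and SAP*

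**What the plan says.** Three sets of statements bear on this.

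- **Period.** Footnote (i) of Section 1.7 reads "Adverse events and SAEs will be followed for 15 days and 30 days, respectively, after the last dose", and for a woman who leaves early it counts from the last dose she had: "after the last received dose in the event of the subject withdrawing". Section 2.4.1 says "Subjects will be monitored for safety and tolerability from Day 1 through 1 month following the third vaccination". Sections 3.4.2.3.1 and 3.5.3.2 set SAE reporting and collection from consent to 1 month after the last vaccination.
- **Last visit.** The Section 1.7 window for Visit 4 is "3 to 7 weeks after Month 6". Table 6 in Section 3.5.4.1 gives the day range for analysis as "21 to 49 after Dose 3", with a target of "30 days after Dose 3". Section 1.4 describes the time point as "approximately 4 weeks after the administration of the third dose". For a woman who discontinues or withdraws, footnote (b) says that, where possible, "all applicable activities scheduled for the final study visit should be performed at the time of discontinuation", apart from the HPV serum sample.
- **How events are found.** The electronic report card runs to Day 15 after each dose. Section 3.4.1 has later conditions asked about at the next scheduled visit, and has women told to contact the investigator at once if they are hospitalized or see another physician. Section 3.4.2.3.1 obliges the investigator to report every SAE in the 1-month period. Outside that period it still requires reporting of vaccine-related SAEs, and of deaths that end participation, if they come to the investigator's attention.

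**The concern.** The period and the schedule do not line up. After Dose 3 the only scheduled occasion for asking about events beyond Day 15 is Visit 4, and a visit fully within the window can come more than a week before the 30 days are over. This need not be rare. A site that books at 4 weeks, as Section 1.4 suggests, sees women on Day 28, which is still short of Day 30. A woman who withdraws may have her last contact earlier still, although footnote (i) states the 30 days for her as well.

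At stake would be an under-count in the summaries that run past Day 15: deaths, serious vaccine-related events at any time during the study, and the remaining SAEs in Tier 3. Safety is a secondary objective, and a reader might take the 30 days to mean that every woman was questioned at the end of them.

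**Working it through.** **Inputs.** SAE period of 30 days after the last dose (Section 1.7, footnote i). Visit 4 at 3 to 7 weeks (Section 1.7). 1 week = 7 days and 1 month = 30 days (Section 1.7, footnote a). Target Day 30 (Table 6). Safety observation of about 7 months (Section 2.4.1). 1,200 women and theoretical incidences for vaccine-related SAEs (Table 9).

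**Reproducing the plan's window.** 3 × 7 = 21 and 7 × 7 = 49, which match Table 6. This also confirms that the window counts from Dose 3.

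**Largest gap for a woman who completes the schedule.** Gap = max(0, 30 − visit day).

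- Visit on Day 21: 30 − 21 = 9 days, or 9/210 = 4.3% of a 7-month (210-day) observation period.
- Visit on Day 28: 2 days.
- Visit on Day 30 to Day 49: none.

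Of the 29 permitted days (21 to 49), 9 leave a gap (21 to 29). If the dose day is counted as Day 1, or a 31-day month is used, the largest gap becomes 8 or 10 days.

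**Average gap.** The documents give no distribution of visit days, so this part rests on assumption: visits within Days 21 to 49, with normal weights on whole days around Day 28 (4 weeks), Day 30 (target) or Day 35 (middle of the window), and a standard deviation (SD) of 3, 5 or 7 days.

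| Centre | Mean gap in days (SD 3 / 5 / 7) | Share seen before Day 30 (SD 3 / 5 / 7) |
|---|---|---|
| Day 28 | 2.40 / 2.53 / 2.39 | 69% / 59% / 52% |
| Day 30 | 1.18 / 1.71 / 1.84 | 43% / 44% / 42% |
| Day 35 | 0.06 / 0.39 / 0.77 | 3% / 13% / 20% |

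If all 29 days were equally likely, the mean gap would be (9 + 8 + … + 1)/29 = 45/29 = 1.55 days, with 9/29 = 31% seen early. The unrounded extremes, 0.057 and 2.535 days, are 0.2% and 8.5% of the 30 days, or 0.03% and 1.2% of the 210 days.

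**Events.** Take the highest incidence in Table 9, 1.0%, so 1,200 × 0.01 = 12 events. Spread them evenly over 210 days and suppose that every event in the gap is missed.

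- Smallest mean gap: 12 × 0.057/210 = 0.003 events.
- Largest mean gap: 12 × 2.535/210 = 0.145, about 0.15 events.
- Every visit on Day 21: 12 × 9/210 = 0.51 events.

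At Table 9's 0.1% the range is one tenth of this, 0.0003 to 0.014. These figures only indicate the order of size. Table 9 concerns vaccine-related SAEs, the class that Section 3.4.2.3.1 makes reportable at any time, and the documents give no incidence for SAEs of any cause.

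**Effort to close the gap by telephone.** A Day 30 call to every woman seen earlier would mean 600 × 0.033 = 20 to 600 × 0.690 = 414 calls per age group, so about 40 to 830 in all, if everyone completes.

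**The case for a change.** The strongest case for acting is that a reporting duty applies only to events the investigator hears of. After an early Visit 4 that depends on the woman coming forward. A target day does not bind a site, whereas the window does, and booking at 4 weeks is fully compliant. The telephone numbers needed for a call are already required by inclusion criterion 7. A cheaper course would be one sentence stating that capture after the last visit rests on reports received, with a count by age group of women last seen before Day 30.

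The factual part stands: for women seen on Days 21 to 29, the last 1 to 9 days are covered passively. The call for action does not. The statements on follow-up, collection and reporting fix a period, and none of them promises scheduled questioning to its end. Capture in the gap is passive but not absent. Hospitalization, itself an SAE criterion, is one of the events for which women are told to contact the site at once. Table 3 also gives later safety follow-up to women found pregnant after Dose 3. The sentence and the count would describe the existing scheme without altering a result.

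Withdrawal is a narrower matter. Women who only stop vaccination keep their visits (Section 3.2.14.1). Section 3.2.14.2 requires withdrawal when consent is withdrawn, and a later call may then not be possible. For these women the gap can exceed 9 days, and a longer schedule would not close it.

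The safety population is worded slightly differently in Sections 2.7.2 (safety follow-up data) and 3.5.4.2 (at least one visit with safety follow-up). That is a separate editorial matter. It affects nobody if Day 1 counts as such a visit, as the safety review listed for Day 1 in the flow chart suggests.

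**Conclusion.** No change is needed. The schedule can leave up to 9 of the 30 days after Dose 3 without scheduled SAE questioning for a woman who completes the study, and none if she is seen on the target day. This is a fair trade-off: one visit serves both serology and safety, and the reporting rules cover the days that may remain. The average shortfall is 0.06 to 2.5 days per woman under the assumed visit timings, and the illustrated under-count stays at or below about 0.15 events in 1,200 (about 0.5 if every visit fell on Day 21). Between 40 and 830 extra calls would be a poor return on that.

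The Tier 2 SAE comparison uses Day 1 to Day 15, which ends before the earliest permitted Visit 4, so it is unaffected, as are the immunogenicity analyses. Both age groups share the same window, so nothing in the plan makes the gap differ between them.

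The day counts follow from the documents. The averages and the event illustration rest on assumed visit timing, an even spread of events, and a theoretical rate for vaccine-related SAEs. The effect on SAEs of any cause cannot be sized from the documents.
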